## **7.2. Withdrawal from the Study**

A participant may withdraw from the study at any time at the participant's request or may be withdrawn at any time for the following reasons:

- At the request of the primary care provider if being in the study is no longer in the best interest of the participant
- Participant is judged by the PI to be at significant risk of failing to comply with the provisions of the protocol as to cause harm to self or seriously interfere with the validity of the study results
- At the discretion of the IRB/IEC or government agencies as part of their duties, PI, or Sponsor.
- The participant progressed to moderate or severe COVID-19 (or worse) prior to initiation of IP dosing on Day 1

If the participant withdraws consent for disclosure of future information, the Sponsor may retain and continue to use any data collected before such withdrawal of consent.

Upon withdrawal from the study, the participant may request destruction of any biological samples taken and not tested, and the PI or designee must document this in the site study records.

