4. INTRODUCTION

The purpose of this statistical analysis plan is to describe the framework for the reporting, summarization and statistical analysis methodology of the safety and efficacy parameters measured for the Gates Medical Research Institute (MRI) study COD-01-T01-01. It is based on Protocol Gates MRI - COD-01-T01-01 Version 4, Amendment 2, 27 January 2021. This study is performed as part of an adaptive, randomized platform core protocol for treatment of early and mildly symptomatic individuals in out-patient settings with severe acute respiratory syndrome coronavirus 2 (SARS-CoV-2) infection. Additional statistical analysis plans will be developed for future protocols and interventions that will be added to the core protocol.

On January 28 and February 3, 2021, the Independent Data Monitoring Committee (IDMC) met to review the available safety and efficacy data to (1) perform the monthly safety review of accumulating data; and (2) evaluate the results of the first prespecified interim analysis for futility. Based on the review of the data, the IDMC determined on February 3, 2021, that the futility boundary was crossed and recommended that the clinical study be stopped. The final statistical analysis plan was amended to reflect changes to the planned analysis following early termination of the study.

As of February 4, 2021, the following changes were made in the study conduct:

- all randomization is ceased and no new study participants are enrolled.
- current participants must discontinue dosing of all study drug and discard their study drug.
- participants should remain in active, masked follow up and continue their study visits until Day 35 if they have had at least one dose of study drug.
 - Participants who have not reached Day 21 will continue safety follow up only until Day 35. These participants will be monitored for AEs, bleeding events and concomitant medication. These participants will not have further assessments for Gates MRI and WHO ordinal scale, symptoms, and nasal swabs for polymerase chain reaction (PCR) test.
 - Participants who have reached Day 21 but not Day 35 of study will continue safety and efficacy follow up until Day 35. These participants will be monitored for AEs, bleeding events, concomitant medication, Gates MRI and WHO ordinal scales, and symptoms. These participants will not have further nasal swabs for PCR test.
- participants who have not yet taken any study drug will discontinue the study early.

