To address potential for substantial under-estimation of the treatment effect, efficacy analyses will be performed on a final efficacy analysis population as described in Section 7.1. Safety analyses will be performed on the Safety analysis population.

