7 STUDY POPULATIONS

7.1 Analysis Populations

An interim analysis was conducted on 28 January, 2021 using the data cut of 8 January, 2021. Efficacy interim analyses were produced based on the first 200 randomized participants who either had discontinued the study or had completed Day 28 in the ITT population. The interim efficacy primary endpoint result will be reported in the CSR using the data cut of 8 January, 2021.

IDMC's recommendation that the clinical study be stopped impacts the efficacy evaluation for the participants who were continuing in the study and had not yet reached Day 21 of the study (end of treatment period) as of 4 February, 2021. In order to have meaningful results of the final efficacy analyses, efficacy analyses will be performed on a final efficacy analysis set of participants who met either one the following criteria:

- Completed or discontinued the study or progressed prior to 5 February, 2021.
- Completed Day 21 or later visits as of 5 February, 2021.

Final analysis will be conducted following database lock.

- Efficacy analyses will be produced for randomized participants who meet the selection criteria described above and also meet the analysis population criteria described below.
- Safety analyses will be produced for all participants in the database who received at least one dose of study intervention.

Table 2: Analysis populations

| Population | Description |
|-------------------|--|
| ITT Population | All participants in the ITT population who met the criteria stated above. Participants will be analyzed according to the intervention to which they were randomized. |
| mITT population | All participants in the ITT population, who received the study intervention and have mild disease at study entry. Participants will be analyzed according to the intervention they actually received. |
| PP population | All participants in the ITT population, who received the study interventions as planned, have mild disease at study entry, and did not substantially deviate from the protocol procedures. Participants will be analyzed according to the intervention they actually received. |
| Safety population | All participants randomly assigned to study intervention, who received the study intervention. Participants will be analyzed according to the intervention they actually received. |

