11.1 Primary Analysis

11.1.1 Estimand

The treatment policy estimand with respect to the primary efficacy objective is defined by the following:

Population: Participants in the ITT population.

Patient-level outcome: Binary outcome of progression to moderate or severe disease category or higher (Gates MRI ordinal scale ≥ 3) at any day through Day 28.

Intercurrent events: The following intercurrent events to be taken into account:

1. If a death occurs on or prior to Day 28, the participant will be considered as having progression to moderate or severe category (Gates MRI ordinal scale ≥ 3) through Day 28.
2. If hospitalization occurs on or prior to Day 28, the participant will be considered as having progression to moderate or severe category (Gates MRI ordinal scale ≥ 3) through Day 28.
3. If a participant is lost to follow-up on or prior to Day 28, the last observed Gates MRI ordinal scale status evaluation will be carried forward onward to Day 28.
4. If a participant discontinues the study prior to initiation of IP dosing on Day 1 (for any reason: lost to follow-up, progression to moderate or severe COVID-19, withdrawal of consent) and no Gates MRI ordinal scale assessment is available, the participant will be considered as having progression to moderate or severe category (Gates MRI ordinal scale ≥ 3) through Day 28.

Participants who discontinue study intervention will be followed at least until end of study, Day 35.

Population-level summary measure: Proportion of participants who progress to moderate or severe disease category or higher (Gates MRI ordinal scale ≥ 3) at any day through Day 28.

The primary efficacy analysis will be conducted in the ITT population. Participants randomized to rivaroxaban will be compared to participants randomized to placebo. For the primary efficacy analysis, the following primary hypothesis will be tested: Prophylactic treatment with rivaroxaban will reduce progression to moderate or severe disease category or greater (Gates MRI ordinal scale ≥ 3) relative to placebo in high risk participants with mild COVID-19.

The proportion of participants who have progression of COVID-19 at any time up to and including Day 28 and the corresponding 2-sided 95% CI, computed using the Mid-p method, will be summarized for the study intervention and control. The absolute difference in the risk of progression of COVID-19 and the corresponding 2-sided 95% CI will be assessed using the

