11.2.1 Estimand

The treatment policy estimand with respect to the secondary efficacy objective is defined for the key secondary endpoints by the following:

Population: Participants in the ITT population.

Patient-level outcome: Time to disease resolution through day 28.

Intercurrent events: The following intercurrent events to be taken into account:

1. If a death occurs prior to Day 28, the participant will be considered as not having disease resolution through Day 28 (i.e., censored at Day 28).
2. If a participant is lost to follow-up prior to Day 28, the participant will be considered as not having disease resolution and will be censored at the time of lost to follow-up.
3. If a participant discontinues the study [for any reason: lost to follow-up, progression to moderate or severe COVID-19 (or worse), withdrawal of consent] prior to initiation of IP dosing on Day 1 and no symptoms resolution assessment is available, the participant will be considered as not having disease resolution and will be censored on Day 1.

Participants who discontinue study intervention will be followed at least until end of study, Day 35.

Population-level summary measure: Median time to disease resolution.

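### Read naturally, the SAP counts an undosed, unscored participant removed only by the 4 February stop as a primary progression event or omits that participant, depending on the recorded exit date

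*SAP*

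**What the plan says.** - **Stop instruction (SAP section 4).** As of 4 February 2021, "participants who have not yet taken any study drug will discontinue the study early".
- **Entry to the final efficacy set (SAP 7.1).** A participant enters by meeting either of two criteria. The first is "Completed or discontinued the study or progressed prior to 5 February, 2021". The second is having completed the Day 21 visit or a later one as of 5 February. The restriction is explained by the effect of the stop on "participants who were continuing in the study and had not yet reached Day 21 of the study (end of treatment period", and SAP section 4 gives its aim as "To address potential for substantial under-estimation of the treatment effect".
- **Outcome rule (SAP 11.1.1, intercurrent event 4, here rule 4).** It covers a study exit "prior to initiation of IP dosing on Day 1 (for any reason: lost to follow-up, progression to moderate or severe COVID-19, withdrawal of consent". It continues: "and no Gates MRI ordinal scale assessment is available, the participant will be considered as having progression to moderate or severe category".
- **Secondary endpoints.** For a similar pre-dose exit, SAP 11.2.1 says "the participant will be considered as not having disease resolution and will be censored on Day 1". SAP Table 3 instead censors randomised, untreated participants at the date of randomisation.
- **Default denominator (SAP 9.2).** Unless stated otherwise, percentages use only participants with non-missing data.

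**The concern.** Rule 4 is a reasonable worst-case convention for someone who worsens or disappears between randomisation and first dose. A participant whom the sponsor removes because the trial has stopped is different: the exit carries no information about disease. Counting it as progression puts a non-clinical event into the primary endpoint, and whether that happens turns on whether an administrative date reads 4 or 5 February.

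What is at stake is the accuracy of the reported progression rates and risk difference in the final ITT analysis. SAP 11.2.4 analyses progression at earlier days in the same way, so those proportions inherit the problem.

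**Working it through.** **Can such participants exist?** Protocol 8.1 has drug sent out after randomisation, and Protocol 3.2.2.1 assumes two days for shipment. The Gates MRI scale is first scheduled on Day 1 (SAP Appendix 1; Protocol 9.1). A randomised participant can therefore be undosed and unscored.

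**Rule trace for one such participant, not progressed, removed only by the stop**

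| Step | Exit recorded 4 February | Exit recorded 5 February or later |
|---|---|---|
| SAP 7.1, criterion 1 | Met | Not met |
| SAP 7.1, criterion 2 | Cannot be met: SAP 9.2 makes Day 1 the first-dose day | Cannot be met |
| Rule 4, any-reason wording taken as general | Progression event | Not analysed |
| Rule 4, three reasons taken as a closed list | No intercurrent-event rule applies; the SAP 9.2 default drops the participant from the proportion | Not analysed |

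Rule 3 (last observation carried forward) cannot help under either reading, because there is no score to carry.

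**Size (illustration only).** The documents give no count.

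Inputs: the design rates of 30% and 19.5% are from SAP 9.1.1. They reproduce its sample size: [1.960 × √(2 × 0.2475 × 0.7525) + 0.8416 × √(0.3 × 0.7 + 0.195 × 0.805)]² / 0.105² = 264 evaluable per arm, and 264/0.9 = 293.3, rounded up to 294 as stated. The 15% rate is the lower control rate used in SAP 11.5.1.1. The figure of 200 per arm is assumed.

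A rough bound on the undosed pool: Protocol 13.2 expected all 600 to be enrolled by the cut for the second interim analysis, which had been planned at about 400 participants past Day 28. That implies about 200 enrolled per 28 days, or 7.1 per day. With a gap of 2 days (shipment, Protocol 3.2.2.1) to 5 days (screening to Day 1, Protocol 8.1), 14 to 36 people would be undosed at the stop. Only those with an exit recorded on 4 February count, so I take 0 to 36 in total.

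With *k* imputed events in an arm, the rate becomes (200·p + k)/(200 + k).

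Even split, rivaroxaban against placebo at 19.5% and 30%:

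| Total exits | Rivaroxaban | Placebo | Difference (points) |
|---|---|---|---|
| 0 | 19.50% | 30.00% | −10.50 |
| 4 | 41/202 = 20.30% | 62/202 = 30.69% | −10.40 |
| 10 | 44/205 = 21.46% | 65/205 = 31.71% | −10.24 |
| 20 | 49/210 = 23.33% | 70/210 = 33.33% | −10.00 |
| 36 | 57/218 = 26.15% | 78/218 = 35.78% | −9.63 |

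At equal true rates an even split changes nothing. At 34.5% against 30%, 20 exits move the difference from 4.50 to 4.29 points (79/210 = 37.62% against 70/210 = 33.33%). That scenario sits near the example futility boundary: p = 0.755 in SAP Table 7 is z = −0.69, and with 100 per arm at an assumed 30%, 0.69 × √(2 × 0.3 × 0.7/100) = 4.5 points against rivaroxaban.

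Chance imbalance at equal true rates:

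- 3:1 of 4 exits at 30%: 63/203 − 61/201 = 31.03% − 30.35% = 0.69 point.
- 14:6 of 20 exits at 30%: 74/214 − 66/206 = 34.58% − 32.04% = 2.54 points.
- 14:6 of 20 exits at 15%: 44/214 − 36/206 = 20.56% − 17.48% = 3.09 points.

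Under independent 1:1 allocation of 20, a split between 6 and 14 has probability 95.9%, so 14:6 is the edge of that range. For scale, the 95% CI half-width 1.96 × √(2p(1 − p)/200) is 8.98 points at 30% and 7.00 at 15%.

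**The case against.** The best reply is that rule 4's three reasons are a closed list. SAP 11.2.1 repeats the same three, and Protocol 7.2 lists a separate ground for withdrawal, "At the discretion of the IRB/IEC or government agencies as part of their duties, PI, or Sponsor". On that view no stop-driven exit becomes an event, and the SAP 9.2 default removes it from the proportion, which is close to what one would want. This is plausible and it stands as an alternative. It does not settle the matter, because the any-reason wording comes before the list and the SAP never says that the list is exhaustive. For the same reason, a reader who infers that the SAP is simply silent on these participants goes too far: each reading leads to a result, but to a different one.

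It also stands that much is already visible. SAP 10.1 reports randomised-not-treated counts and reasons for discontinuation by arm, and the mITT and PP repeats in SAP 11.1.2 exclude everyone undosed.

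A reader might also draw three stronger inferences, which the documents do not support:

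- **That the trial's conclusion is affected.** The futility boundary was binding (SAP 11.5.1) and was crossed on the 8 January data cut (SAP 7.1), before any of these exits.
- **That statistical significance could be lost.** With 150 per arm at about 19.5% against 30% and a 7:3 imbalance against rivaroxaban, the one-sided p does move from 0.016 to 0.048. That needs the full design effect in a trial whose interim result crossed a boundary lying, in the Table 7 example, on the side of harm.
- **That only the progression endpoints are involved.** The 5 February cut-off decides entry to every efficacy analysis. What is particular to progression is that the exit becomes an event; the resolution endpoints censor it.

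**Conclusion.** The point holds as a minor one. On its natural reading, rule 4 combined with SAP 7.1 and the stop instruction turns a purely administrative exit dated 4 February into a primary progression event and omits the identical exit dated later. On the closed-list reading the participant falls out of the proportion by default. The SAP should say which applies.

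The effect is probably small. An even split dilutes the design difference by 0.5 point for 20 exits and 0.9 for 36. Imbalance could move the difference either way, by about 2.5 to 3.1 points in the 14:6 examples, well inside the confidence interval. These figures assume 200 per arm and an unknown count that may be zero. A reader might infer a serious conflict with the SAP's aim of avoiding substantial under-estimation; the direction of dilution does run against that aim, but the size does not support the word substantial.

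Rule 4 itself is not in dispute for documented pre-dose progression or for ordinary pre-dose losses.

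**What to change.** 1. **SAP 7.1, one sentence.** Undosed participants with no Gates MRI score whose only reason for leaving is the 4 February stop are excluded from the final efficacy set, whatever their recorded exit date. Rule 4 then never reaches them, and SAP 11.1.1 needs no further wording.
2. **Leave rule 4 as written** for participants withdrawn before dosing for other reasons before the stop, including the documented progression described in Protocol 7.2. Do not add a separate route that admits stop-driven exits only if they progressed, since that group could then enter only as events.
3. **Report** the number of rule 4 imputations by arm and reason with the disposition table planned in SAP 10.1.
4. **Reconcile** the censoring date for untreated participants between SAP 11.2.1 (Day 1) and Table 3 (randomisation).

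The cost is a few lines of SAP wording and one table line, with no new data. Protocol 10.5 has the SAP final before database lock; if lock has passed, the handling and the count belong in the clinical study report, as Protocol 11.5 provides for deviations.

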## 5. Study Design

### 5.1. Overall Design

This is a randomized, controlled study for treatment of mild COVID-19 in people at high risk for disease progression.

Mild COVID-19 is determined by Gates MRI mild COVID-19 clinical endpoint definition (refer to [Table 7](#)).

High risk is defined based on age, BMI or presence of a comorbidity.

**Primary purpose:** To assess the safety and clinical efficacy of rivaroxaban in reducing the proportion of participants who have progressed to moderate or severe disease category or higher in people with mild COVID-19 who are at increased risk of disease progression.

**Interventional model:** Participants will be randomized 1:1 to either the rivaroxaban or the placebo group, in parallel for the duration of the study. Randomization will be stratified by site and by number of days since onset of symptoms (<6 days vs.  $\geq 6$  days).

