**Figure 3: Randomization strategy for sites where 3 interventions are being studied**

**Figure 4: Randomization strategy for sites where 2 interventions are being studied**

**Figure 5: Randomization strategy for sites where only 1 intervention is being studied**

#### 10.4. Primary and Key Secondary Endpoints

The primary efficacy endpoint is the proportion of participants who progress to moderate or severe disease category or higher (Gates MRI ordinal scale  $\geq 3$ ) through Day 28.

Secondary efficacy endpoints include time to disease resolution, defined as symptoms resolution with or without viral clearance, proportion of participants with disease resolution, Gates MRI and WHO ordinal scales, and incidence and duration of hospitalization.

Primary safety endpoints include the frequency of Grade 3 and Grade 4 AEs, AEs resulting in study intervention discontinuation and SAEs.

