9 OVERALL STATISTICAL CONSIDERATIONS

9.1 Determination of Sample Size

9.1.1 Efficacy

The total number of participants planned to be enrolled is approximately 600 (300 per group). If the true control rate for progression to moderate or severe category or greater is at least 30%, 294 participants per group will result in 80% power when the true study intervention effect is 35% as a relative decrease of rate progression, i.e., a true rivaroxaban rate of progression of 19.5% is 35% lower than that of a true placebo-control rate of progression of 30%. This sample size accounts for a drop-out rate of 10% and a 1-sided Type I error rate of 2.5%. To account for one planned interim futility analysis without adversely affecting the statistical power, the sample size was increased to 300 per group.

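### SAP 11.1.1 counts every unscored exit before the first dose as COVID-19 progression, including simple loss to follow-up and withdrawal of consent

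*SAP*

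**What the plan says.** Protocol 10.4 defines the endpoint: "The primary efficacy endpoint is the proportion of participants who progress to moderate or severe disease category or higher", through Day 28. It says nothing about participants who never start treatment, and Protocol 10.5 leaves missing data to the SAP.

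SAP 11.1.1 analyses the ITT population and lists four intercurrent events. The first two make death or hospitalization by Day 28 an event. For loss to follow-up by Day 28, rule 3 says that "the last observed Gates MRI ordinal scale status evaluation will be carried forward onward to Day 28". Rule 4 covers a participant who leaves the study before taking any study drug, with this condition: "for any reason: lost to follow-up, progression to moderate or severe COVID-19, withdrawal of consent) and no Gates MRI ordinal scale assessment is available". Such a participant is scored as progressed.

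The secondary estimand treats the same people differently. SAP 11.2.1 censors them on Day 1, and SAP Table 3 censors the randomized but untreated at randomization.

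SAP 11.1.2 repeats the primary analysis in the mITT and PP populations and with actual strata. The document history (SAP Appendix 5) records that sensitivity analyses 1 to 3 of the primary endpoint were dropped in Version 2.0.

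**The concern.** Loss to follow-up and withdrawal of consent are reasons for missing data. Rule 4 records them as the outcome, in the same class as true progression before dosing. The SAP gives no reason for doing so in the primary analysis while treating the same exits as censored in the secondary one.

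The rule can be expected to apply. Both schedules of activities place the first Gates MRI score on Day 1. Randomization is at screening, up to 5 days before Day 1, and Protocol 3.2.2.1 allows two days for shipping study drug. Anyone who leaves in that gap will normally have no score. SAP 10.1 already plans a count of participants randomized and not treated.

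At stake are the reported progression rates, the precision of the risk difference and its sensitivity to a chance imbalance in non-starters. No remaining ITT analysis scores these participants in any other way.

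**Working it through.** **Inputs.** Three come from SAP 9.1.1. On effect and power, it says "294 participants per group will result in 80% power when the true study intervention effect is 35% as a relative decrease of rate progression". On event rates, it gives "a true rivaroxaban rate of progression of 19.5% is 35% lower than that of a true placebo-control rate of progression of 30"%. On loss and error rate, it states "This sample size accounts for a drop-out rate of 10% and a 1-sided Type I error rate of 2.5"%. Planned size is 300 per group. The share q of participants who leave before dosing, unscored, for reasons other than progression is not in the documents. I take 1% to 5% as an assumption.

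**The plan's own figure.** With pooled variance under the null and mean rate 0.2475:

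n = [1.960 × √(2 × 0.2475 × 0.7525) + 0.842 × √(0.30 × 0.70 + 0.195 × 0.805)]² / 0.105² = 264 per arm.

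264 / 0.90 = 293.3, so 294. The SAP figure reproduces; the sample size itself is not in question. With 300 per arm and no loss, power is 84.8%.

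**Three ways to score non-starters**, for an arm with true rate p:

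- Rule 4: q + (1 − q)p.
- Fully observed, non-starters progressing at 30% in both arms: 0.30q + (1 − q)p.
- Non-event: (1 − q)p.

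Power = Φ{[d − 1.960 × √(2p̄(1 − p̄)/n)] / √[(pC(1 − pC) + pT(1 − pT))/n]}, with n = 300, d the difference in rates and p̄ their mean.

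**Example, q = 5%.**

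- Rule 4: 33.5% vs 23.5%, difference 9.98 points, SE 3.66 points, power 77.4%.
- Observed: 30.0% vs 20.0%, difference 9.98 points, SE 3.51 points, power 80.7%.
- Non-event: 28.5% vs 18.5%, difference 9.98 points, SE 3.44 points, power 82.3%.

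The difference is 0.95 × 10.5 points in all three. It shrinks because non-starters are untreated, not because of rule 4. What rule 4 changes is the level of the rates and the standard error.

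| q | Rule 4 | Observed at 30% | Non-event | Cost of rule 4 (points) |
|---|---|---|---|---|
| 1% | 83.3% | 84.0% | 84.3% | 0.7 to 1.0 |
| 2% | 81.9% | 83.2% | 83.8% | 1.3 to 1.9 |
| 3% | 80.4% | 82.4% | 83.3% | 2.0 to 2.9 |
| 5% | 77.4% | 80.7% | 82.3% | 3.3 to 4.9 |

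These rows assume no other loss. If total loss is the planned 10% and the other losses are excluded, the q = 5% figures are 74.8% (rule 4) and 80.2% (non-event). The level is lower and the gap similar.

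**Event counts at q = 5%.** Rule 4 adds 300 × 0.05 = 15 events per arm. In the control arm that is 0.05 / 0.335 = 15% of all reported progressions. If these people truly progress at 30%, 4.5 of the 15 are right and 10.5 are not.

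**Imbalance.** Five more non-starters in one arm move the risk difference by 5/300 = 1.7 points compared with scoring them as non-events. Compared with true progression of 30%, the shift is 5 × 0.70/300 = 1.2 points.

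**Type I error.** In 400,000 simulated trials per setting (unstratified Miettinen-Nurminen score test, 30% true progression in both arms, equal exits), one-sided error was 2.46% at q = 2%, 2.52% at 5% and 2.49% at 10%.

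**The case against.** The rule is explicit, applies to both arms alike and is conservative for a superiority test. Protocol 10.5 entitles the SAP to set it. The mITT and PP analyses remove every non-starter, and disposition by arm would show an imbalance. Loss just before dosing may also be informative: Protocol 3.2.2.1 puts the first dose at up to about 9 days from symptom onset and expects progression mainly on Days 8 to 12. Scoring every such loss as a non-event would therefore be biased too.

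Most of this stands, and it limits the point. It does not justify imputing certain progression in the primary analysis. The mITT and PP analyses also change the population and analyse by treatment received, so they do not isolate the effect of the rule.

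A reader might infer that these participants were confirmed mild at screening, so that rule 3 could simply be applied to them. The documents do not support that. Protocol 5.1 says "Mild COVID-19 is determined by Gates MRI mild COVID-19 clinical endpoint definition", and that scale is first scored on Day 1. The hypoxemia exclusion applies at Day 1, and the oximeter is sent after eligibility is confirmed. There is no score to carry forward, and rules 3 and 4 cover different data situations.

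A reader might also infer that rule 4 dilutes the treatment effect. The relative risk does move, from 0.65 to 0.70 at q = 5%. The planned measure is the risk difference, which is the same under all three scorings.

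**Conclusion.** The point holds as a fault in the imputation rule, of modest and unknown size. Rule 4 turns exits unrelated to disease into primary progression events, raises both reported rates and widens the interval for the risk difference. The cost in power is about 1 point at q = 1% and 3 to 5 points at q = 5%. With no other loss, power falls below 80% once q is just over 3%. All of this rests on an assumed q, the design rates and 300 per arm. Randomization has stopped, so for this trial the rates and interval matter more than the power.

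Two stronger readings are not supported. The first is that the rule drove the futility result. The documents give no count of non-starters. Under the design effect, with 100 per arm and the boundary p-value of 0.7550 in SAP Table 7, a normal approximation gives a crossing probability of 0.8% with no non-starters and 1.2% at q = 5%. The second is that participants still undosed at the February 2021 stop became events. The SAP gives neither their number nor their recorded exit dates, and a sponsor stop is not among the reasons that rule 4 lists.

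**What to change.** Limit rule 4 to pre-dose exits with documented progression to moderate or severe disease, hospitalization or death. Handle all other unscored pre-dose exits by one stated missing-data rule. This could be multiple imputation, or non-event declared as an assumption because neither a Gates MRI score nor oxygen saturation is taken at screening. The same text should say how withdrawal of consent after Day 1 is scored, since rule 3 names only loss to follow-up.

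Keep the all-events rule as a worst-case sensitivity analysis in the ITT population, and report non-starters by arm and reason.

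Discontinuation reasons are already on the eCRF (SAP 10.1), so the work is SAP wording and one extra run, plus the imputation model if that option is taken. There are two drawbacks: the primary analysis becomes slightly less conservative, and the change comes after the interim analysis. It should therefore be made before unblinding for the final analysis and its result shown beside that of the current rule.
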